4 SELECTION AND ENROLLMENT OF SUBJECTS

4.1 Inclusion Criteria

1. Men or women aged 40 and older with the diagnosis of idiopathic PD per UK Brain Bank criteria
2. Hoehn-Yahr Stage I-III, on stable dopaminergic treatment regimen for \geq 4 weeks prior to baseline.

4.2 Exclusion Criteria

1. Subjects unwilling or unable to give informed consent
2. Secondary parkinsonism (e.g., drug induced)
3. Parkinson-plus syndromes
4. History of brain surgery for PD such as deep brain stimulation
5. No confounding acute or unstable medical, psychiatric, orthopedic condition. Subjects who have hypertension, diabetes mellitus, depression, or other common age-related

FAST TZ-PD

Version 1.8

Version date: 2/7/2019

illness will be included if their disease under control with stable treatment regimen for at least 30 days.

6. Neurogenic orthostatic hypotension defined as symptomatic decrease in BP > 20mmHg systolic or > 10mmHg diastolic and HR increase < 20bpm on supine to sitting or standing.
7. Clinically significant traumatic brain injury or post-traumatic stress disorder
8. Presence of other known medical or psychiatric comorbidity that in the investigator's opinion would compromise participation in the study
9. Presence of dementia per Movement Disorder Society Level I criteria
10. Major depression, bipolar affective disorder, or other mental health disorders that are sufficiently severe to increase adverse event risk or impact neuropathy assessment in the opinion of the responsible site principal investigator.
11. Current suicidal ideation within one year prior to the baseline visit as evidenced by answering "yes" to Questions 4 or 5 on the suicidal ideation portion of the Columbia-Suicide Severity Rating Scale (C-SSRS), Beck Depression score >21, Beck Anxiety score >22.
12. History of exposure to typical or atypical antipsychotics or other dopamine blocking agents within 6 months prior to the baseline visit
13. Use of investigational drugs within 30 days before screening
14. Subjects have to be on a stable regimen of central nervous system acting medications (benzodiazepines, antidepressants, hypnotics) for 30 days prior to the baseline visit
15. Use of doxazosin, alfuzosin, prazosin, or tamsulosin
16. For female participant, pregnancy, or plans for child-bearing during study period
17. Participant is restricted from traveling to and from the study site

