We will randomize 20 PD patients to receive TZ or placebo. Ten of the participants will be randomized to receive TZ 5mg daily for 12 weeks and 10 participants will be randomized to receive a daily placebo for 12 weeks. This aim will generate data on safety and tolerability of TZ in a population of patients with PD. As an exploratory outcome, we aim to determine if treatment with TZ in patients with PD improves markers of energy metabolism. Furthermore, we will determine if cellular and cerebral ATP levels correlate with disease severity and progression. Participants will also participate in an assessment that will include, but is not limited to a motor exam, a neuropsychological assessment, and functional assessments. Clinical findings will be used to guide future clinical trials.

Interventions and Duration

Participants in this study will be randomized to receive either TZ 5 mg by mouth once daily or a matched placebo once daily. Once randomized, each participant will receive their assigned treatment for 12 weeks. Participants will be assessed via telephone for 3 weeks after their 2 week visit, then 6 weeks months after their baseline visit, then via telephone 9 weeks after their baseline visit, and their last visit will occur 12 weeks from their baseline visit. We anticipate that this study can be completed (study open to end of data analyses) within 9 months.

Sample Size and Population

This study will randomize 20 participants: 10 participants will be randomized to receive 5mg of TZ daily and 10 participants will be randomized to the placebo group. It is anticipated that no more than 35 participants will need to be screened to enroll these participants.

This study will include participants who are ≥ 40 years old who have a confirmed diagnosis of PD made by a neurologist and a Hoehn & Yahr score at baseline of < 4 . Participants will be excluded from this study if any of the following are true:

- Participants has orthostatic hypotension or a sitting blood pressure of $\leq 90/60$
- Participant is pregnant
- Participant has a deep brain stimulation device implanted
- Participant has a known allergy or sensitivity to terazosin
- Participant is concomitantly taking doxazosin, alfuzosin, prazosin, urapadil, or tamsulosin
- Participant has active drug or alcohol use or dependence that, in the opinion of the site investigator, would interfere with adherence to study requirements
- Participant is unable or unwilling to give written informed consent

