4.5 Study Enrollment Procedures

Only subjects who meet all the inclusion and none of the exclusion criteria will be eligible for enrollment and subsequent randomization in the study. No protocol waivers will be allowed for eligibility criteria. Subjects will be deemed eligible for enrollment by the PI. If eligible for enrollment, the site investigators will review the informed consent documents with the subject. If

the subject signs the informed consent document, they will be considered as being enrolled in the study.

Once a participant has been enrolled, they will be assigned a Subject Identification Number by the site. After a subject is enrolled and has a Subject Identification Number, they will undergo a screening visit. If they fail the screening, their Subject Identification Number will be documented and their reason for screening failure will be documented. If a subject fails their initial screening visit, they will not be eligible for re-screening for the study. If a subject is deemed eligible after their screening visit, they will be randomized to treatment.

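### The exclusion list in Section 4.2 conflicts with the synopsis and the drug-stopping rules on orthostatic hypotension and low blood pressure, so a site working from 4.2 could randomize someone who already meets a stopping rule

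*Combined protocol and SAP*

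**What the plan says.** Section 4.5 ties entry to the criteria and allows no waivers: "Only subjects who meet all the inclusion and none of the exclusion criteria will be eligible for enrollment and subsequent randomization in the study".

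On OH, Section 4.2 item 6 reads "Neurogenic orthostatic hypotension defined as symptomatic decrease in BP" and continues with a fall of more than 20 mmHg systolic or more than 10 mmHg diastolic, a heart-rate increase below 20 bpm, and a change from supine to sitting or standing. None of the 17 items sets a resting blood-pressure floor. Item 8, "Presence of other known medical or psychiatric comorbidity", leaves other conditions to the investigator's opinion.

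The synopsis (Sample Size and Population) has its own mandatory list. It includes "Participants has orthostatic hypotension or a sitting blood pressure of" 90/60 or lower, with no symptom or heart-rate condition. It also includes "Participant has a known allergy or sensitivity to terazosin", which 4.2 lacks.

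Footnote a to the Schedule of Activities (6.1) classes a participant as having OH if systolic pressure falls by 20 mmHg or more, or diastolic by 10 mmHg or more, after 3 minutes standing. Sections 6.2.3 and 8 both stop study drug if OH is present or if pressure is 90/60 or lower, again without reference to symptoms.

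The alpha-blocker lists also differ. Item 15 of 4.2 says "Use of doxazosin, alfuzosin, prazosin, or tamsulosin". The synopsis says "Participant is concomitantly taking doxazosin, alfuzosin, prazosin, urapadil, or tamsulosin". Section 5.3.2 prohibits those five drugs and terazosin itself.

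**The concern.** Section 2.3 singles out OH as especially important in this population. The entry rule for it ought to be at least as strict as the rule that stops the drug, and in 4.2 it is looser. A participant could take a first dose when the protocol already requires the drug to be stopped. If that is missed on Day 1, the next scheduled orthostatic measurements are at week 2, when the titration table in 5.1 has reached two 1 mg capsules a day.

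There is also a cost to interpretation. Section 9.4 compares OH prevalence between groups by chi-square with no baseline adjustment, and 6.3.8 concedes that the assessment cannot separate a drug effect from autonomic failure. Someone who enters with OH is counted as a case whichever treatment they receive, and adds noise to the drug-stop rate. They add to drop-out, part of the primary outcome, only if they also leave follow-up: 6.2.4 and 8 ask or encourage them to stay, while 6.2.3 says they need not.

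**Working it through.** The plan gives no figure for this point, so the check is mainly a comparison of text.

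| Feature | 4.2 | Synopsis | Footnote a | 6.2.3 and 8 |
|---|---|---|---|---|
| Symptoms required for OH | Yes | No | No | No |
| Heart-rate condition | Rise below 20 bpm | None | None | None |
| Size of fall | Above 20 or above 10 | Not given | 20 or more, or 10 or more | Not given |
| Posture | Supine to sitting or standing | Not given | 3 minutes standing | Not given |
| Pressure at or below 90/60 | No rule | Excluded (sitting) | Not applicable | Stops drug |

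Four cases follow, reading OH in the stop rules by footnote a, the only general definition given:

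1. An asymptomatic 25 mmHg systolic fall on Day 1 passes item 6 because there are no symptoms, and meets the stop rule.
2. A sitting pressure of 88/58 meets no specific item in 4.2, and meets the stop rule.
3. A symptomatic 25 mmHg fall with a heart-rate rise of 20 bpm or more passes item 6, and meets the stop rule.
4. A fall of exactly 20 systolic passes item 6, which requires more than 20, and meets the stop rule.

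The synopsis bars case 2 outright. It bars the other three if its unqualified OH is read by footnote a.

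**Size per person.** With 10 per arm, one such person counted as a case is 1/10 = 10 percentage points of that arm's OH prevalence or drug-stop rate.

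**Screening cost.** The synopsis states: "It is anticipated that no more than 35 participants will need to be screened". That means 35 screened for 20 randomized, with 35 − 20 = 15 failures for all reasons. Let p be the share of otherwise eligible people who pass 4.2 but fail the aligned rule. The documents do not give p, so it is an assumption. Screens needed become 35/(1 − p), and the extra is 35/(1 − p) − 35 = 35p/(1 − p).

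- p = 1%: 35 × 0.01/0.99 = 0.35, about 0.4
- p = 5%: 35 × 0.05/0.95 = 1.84
- p = 10%: 35 × 0.10/0.90 = 3.89
- p = 20%: 35 × 0.20/0.80 = 8.75

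Because 35 is the stated ceiling, any of these would exceed it if the other failures already use all 15 places. If sites already apply the synopsis, the extra is zero.

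**The case against.** The strongest reply is that the synopsis belongs to the same protocol and is mandatory. Section 4.5 speaks of the exclusion criteria without limiting them to 4.2. Orthostatics are done at screening and again on Day 1 before randomization, recruitment is through one university's clinic and referrals, and the PI decides eligibility. This largely stands against a stronger statement that a reader might infer, namely that the protocol as a whole admits people with OH. It does not: read together, its parts exclude them. What remains is that the section headed as the exclusion criteria says something different, and nothing states which list governs. Item 8 allows an investigator to exclude such a person but names no limit.

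A reader might infer from 4.4, whose example is persistent symptomatic OH, that symptoms were meant to be required throughout. The stop rules in 6.2.3 and 8 are unqualified and appear twice, so the text does not support that. Nor can 4.4 be set aside as concerning only departure from the study: it turns on whether continuing treatment poses undue risk, so it overlaps with the automatic stop.

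A reader might also infer a biased comparison. These people would be randomized like everyone else and fall in either arm by chance. Probabilities of imbalance would rest on assumed counts and describe ordinary chance variation.

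The allergy, terazosin and urapadil omissions are lesser matters. The synopsis covers allergy and urapadil, 5.3.2 names terazosin and urapadil, and 6.2.1 reviews prohibited medications at screening.

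Finally, 4.2 is not narrower everywhere. It adds dementia, antipsychotic exposure and suicidality, and item 6 also looks at sitting. A page break inside 4.2 carries a Version 1.8 stamp while other pages show Version 2.0. That may indicate text that was not updated, but does not prove it.

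**Conclusion.** The contradiction is real and should be corrected. On OH and low blood pressure, 4.2 is looser than both the synopsis and the stop rules, and a site that follows 4.2 alone could randomize someone who already qualifies for stopping the drug. The 10-point effect per person assumes 10 per arm and that the person is counted as a case. The documents give no basis for saying how many there would be, and the number is zero if the synopsis is applied in practice. This is a safety inconsistency and a source of noise in a small trial. It is not a demonstrated bias, and it does not undermine the design. The drug and allergy gaps are housekeeping.

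**What to change.** - In 4.2, replace item 6 with an exclusion for any fall meeting footnote a at screening or Day 1, with or without symptoms and whatever the heart rate. Keep the supine-to-sitting check.
- Add to 4.2 a sitting pressure at or below 90/60, so that entry matches the synopsis and the stop rules.
- As minor alignment, add terazosin allergy or sensitivity to 4.2, extend item 15 to terazosin and urapadil, and add terazosin to the synopsis drug list.
- Leave the stop rules in 6.2.3 and 8 unchanged. Limiting them to symptomatic cases would keep people with silent falls on a drug whose main named risk is OH.
- State in 4.4 that, for OH and low pressure, those rules apply automatically and take precedence over the site PI's discretion.

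The cost is a wording amendment plus the extra screening derived above. At the upper end of the assumed range, the sponsor should expect that the planned 35 may not be enough, and should revise that figure.

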4.3 Lifestyle Considerations

No specific restrictions on lifestyle and/or diet will be placed on the subject during the study. If a participant is prescribed an α-1 antagonist that is indicated for their care, they will be withdrawn early from the study to 1) avoid the risk for harmful side effects and 2) to maintain the integrity of blinding.

4.4 Subject Withdrawal Criteria

Subjects are free to withdraw from the study at any point. Subjects will be withdrawn from the study if they experience serious and/or persistent side effects during the study that, in the opinion of the site PI, are thought to be related to the study drug. Examples include but are not limited to persistent and symptomatic orthostatic hypotension, persistent peripheral edema, persistent drowsiness that significantly affects activities of daily living, significant weakness, or falls. If any of these side effects occur, the site PI will be asked to make a recommendation regarding whether continuation of the study treatment will place the subject at any undue risk. If so, the subject will be immediately withdrawn from the study.

Withdrawn subjects will not be replaced. Should a subject withdraw from the study despite all efforts to maintain follow-up every effort should be made to obtain an in-person final visit, which should include all assessments that would be obtained in the final drug visits (see Section 6).

4.5 Study Enrollment Procedures

Only subjects who meet all the inclusion and none of the exclusion criteria will be eligible for enrollment and subsequent randomization in the study. No protocol waivers will be allowed for eligibility criteria. Subjects will be deemed eligible for enrollment by the PI. If eligible for enrollment, the site investigators will review the informed consent documents with the subject. If

the subject signs the informed consent document, they will be considered as being enrolled in the study.

Once a participant has been enrolled, they will be assigned a Subject Identification Number by the site. After a subject is enrolled and has a Subject Identification Number, they will undergo a screening visit. If they fail the screening, their Subject Identification Number will be documented and their reason for screening failure will be documented. If a subject fails their initial screening visit, they will not be eligible for re-screening for the study. If a subject is deemed eligible after their screening visit, they will be randomized to treatment.

4.5.1 Subject Recruitment and Retention

Subjects will be recruited from the University of Iowa Neurology clinic as well as from referrals from other providers within the University of Iowa.

4.5.2 Screening Logs

Screening logs will be collected for all enrolled participants. Screening logs to document reasons for ineligibility and reasons for nonparticipation of eligible subjects will be stored by the PIs. Screening logs of all participants will include information regarding how the subject learned of the trial, reasons for screen failure (if applicable), and reasons for not participating in study (if applicable).

4.5.3 Informed Consent

Written informed consent will be obtained from each study subject before any study-specific procedures or assessments are done and after the aims, methods, anticipated benefits, and potential hazards are explained. The subject's willingness to participate in the study will be documented in writing in a consent form approved by the IRB at the University of Iowa, which will be signed by the subject with the date of that signature indicated. The investigator will keep the original consent forms and a copy will be given to the subject. It will also be explained to the subject that they are free to refuse entry into the study and free to withdraw from the study at any time without prejudice to future treatment. Written and/or oral information about the study in a language understandable by the subject will be given to all subjects.

If a participant is unable to read the consent forms, the consent form will be read in its entirety to the subject. If the subject is willing and able to provide verbal consent to participate in the study, but is physically unable to provide their signature, the subject's authorized representative may sign the subject's name while also providing their name and relationship to the study participant.

4.5.4 Randomization/Treatment Assignment

Participants will be randomized in a 1:1 fashion to TZ 5mg daily and placebo. Randomization will be performed by NuCara Pharmacy in Coralville, Iowa. Randomization codes will be made available only to the dispensing pharmacist. The randomization code will not be made available to the investigators, study centers, study subjects, or other representatives. Only after the study is complete, will randomization codes be made available to the investigators.

5 STUDY INTERVENTIONS/STUDY MEDICATION/STUDY DRUG OR DEVICE

5.1 Study Medications/Interventions, Administration, and Duration

Once randomized, all participants will receive a one-month titration packet. For participants who are randomized to receive TZ, it is important to titrate the dose slowly to avoid higher incidences of orthostatic hypotension. All participants will undergo a dummy titration schedule to maintain blinding. The titration schedule is outlined below:

	Placebo	TZ 5mg per day
Week 1 (days 1-7)	P	A
Week 2 (days 8-14)	P + P	A + A
Week 3 (days 15-21)	P + P + P	A + A + A
Week 4 (days 22-28)	P + P + P + P	A + A + A + A
Day 28 and beyond	P	AA

P = 1 Placebo Capsule

A = 1 capsule containing 1mg of TZ

AA = 1 capsule containing 5mg of TZ

Participants will be informed of the titration schedule at randomization and all participants will be informed that they will be switched to a single capsule starting on Day 28 and beyond. This will maintain blinding and avoid the need for participants to have a 4 capsule pill burden for the remainder of the study.

Participants will be provided with the entire study supply of 1mg and 5mg terazosin or placebo. The first bottle will contain a one month supply of 1mg capsules for the titration period. The second bottle will contain a two month supply of 5mg capsules. The participant will be instructed to take their dose of medication once daily. The participant will be instructed to take their dose of medication before bedtime to maintain the same dosing schedule, as doses should be separated by at least 23 hours. Each treatment will be administered by the participant in their home by mouth. Each participant will be maintained on their dosage schedule for the duration of the study (3 months). Dose escalation schedules will not be employed.

5.2 Handling of Study Medications/Interventions

Study treatment will be compounded and shipped to the University of Iowa IDS Pharmacy by NuCara Pharmacy. All treatment capsules will be compounded to have similar appearance, color, taste, and markings between active treatment capsules and placebo capsules. The NuCara Pharmacy will be responsible for all regulatory requirements for dispensing of treatment, including packaging and labeling requirements. Additionally, the NuCara Pharmacy will be responsible for documenting the codes of the treatment bottles that are dispensed.

On Day 1 of the study, the participant will be given a 1 month supply for their initial titration medication, either terazosin or placebo per randomization, and a 2 month supply of the 5mg capsules. At each visit, participants will bring their medication bottles to the investigator who will be responsible for counting the remaining capsules and checking medication compliance.

An investigator is responsible for ensuring product accountability records are maintained throughout the course of the study. The inventory will include details of treatment bottles received and dispensed to subjects, batch, and ID numbers. All unused capsules must be kept until reconciliation of delivery records with accountability logs by the monitor. An accounting must be made of any drug deliberately or accidentally destroyed. Discrepancies between the number of capsules received and dispensed drug must be reconciled.

5.3 Concomitant Interventions

5.3.1 Required Concomitant Medications/Interventions

No specific concomitant medications/interventions are required for this study. Participants will continue to receive their normal level of care from their providers, and any concomitant medications initiated by outside providers will be dispensed by the subject's preferred pharmacy. Any time that a new medication is prescribed to a participant, they are to contact their site to report this change in therapy to ensure that it is allowed.

5.3.2 Prohibited Medications/Interventions

Subjects are prohibited from taking doxazosin, alfuzosin, prazosin, terazosin, urapadil, or tamsulosin during this study. If one of these medications is prescribed during the course of the study, the participant will be informed that initiation of any of these treatments will result in their immediate withdrawal from the study. They may decide if they wish to receive the prescribed treatment from their outside provider. If the subject decides to not initiate the prohibited treatment, they may remain in the study.

5.4 Subject compliance

Subject compliance will be assessed at each study visit via pill counts. Specifically, study intervention will be dispensed in prescription bottles and subjects will be asked to bring their bottles to each visit so that compliance can be assessed. See section 5.2 for additional information.

